### **2.4 Study Populations**

Participants suitable for this protocol are individuals with chronic HF who are hospitalized with acute heart failure, have achieved clinical stability and have an LVEF  $\leq 35\%$  and heart-rate  $\geq 70$  bpm in normal sinus rhythm. Participants should not have a planned/scheduled up titration of

beta-blocker in the following 4 weeks. Adjustments of background therapy can be made at any point during the study period at the discretion of the attending physician.

All participants randomized to the study constitute the intent to treat (ITT) population.

Participants that receive ivabradine at the week 6 visit constitute the treated population. The primary efficacy endpoint will be evaluated based on the ITT population. As a sensitivity analysis, the primary and key secondary endpoints will be evaluated on the treated population.

## **2.5 Study Endpoints**

### **2.5.1 Primary Endpoint**

The study protocol (in section 10.1) states that the primary endpoint of the study is the proportion of participants using ivabradine at 180 days. The endpoint for each participant will be determined from ivabradine use at 180 days evaluated as a binary outcome.

### **2.5.2 Secondary Endpoints**

The secondary endpoints are:

- 1) Heart rate assessments
  - a) Change in heart rate from baseline to 180 days
  - b) Heart rate at 180 days
  - c) Proportion of participants with heart rate < 70 bpm at 180 days
- 2) Change in symptoms and quality of life from baseline to 180 days as assessed by:
  - a) KCCQ
  - b) PGA

### 2.5.3 Tertiary endpoints

Tertiary endpoints are

- 1) Beta-blocker use at 180 days as assessed by the:
  - a) Proportion of participants on beta-blocker at 180 days
  - b) Proportion on target dose
  - c) Proportion discontinuing beta-blockers at 180 days and
  - d.) Mean change in beta-blocker dose from discharge to 180 days.
- 2). Ivabradine use at 180 days as assessed by the:
  - a) Proportion of appropriate participants with any initiation of ivabradine at 180 days
  - b) Proportion of appropriate participants at the maximum dose of ivabradine at 180 day.
  - c) Mean dose of ivabradine achieved at 180 days.
- 3). Tolerability of ivabradine and events of interest:
  - a) Symptomatic bradycardia
  - b) Symptomatic hypotension
  - c) Other symptoms leading to ivabradine discontinuation
- 4). Summary of barriers to acquisition of ivabradine

---

 Beta-blocker target dose is defined as participants who receive Carvedilol equivalent total daily dose of 50 mg

 Appropriate participants are defined as participants who have a sinus rhythm (participants excluding those with AF) and heart rate of  $\geq 70$  bpm. For participants missing 180 day ECG, results from the baseline ECG are used to determine appropriateness.

 Receiving ivabradine at any time point during the study.

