## PRIME-HF

- 
- 5) Age  $\geq 18$  years
  - 6) Willingness to provide informed consent from the subject (or at the discretion of the local IRB, the subject's guardian or legally authorized representative [LAR])
  - 7) On the day of planned randomization, all participants:
    - Must be in sinus rhythm with a resting heart rate  $\geq 70$  bpm as measured on ECG or a 10 second rhythm strip
    - Must have a blood pressure of  $\geq 90/50$  mm Hg

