**Table 1. Recommended Dose Adjustments for Patients Taking Ivabradine**

Heart Rate	Dose Adjustment
>60 bpm	Increase dose by 2.5 mg (given twice daily) up to a maximum dose of 7.5mg twice daily
50-60 bpm	Maintain current dose
<50 bpm or signs and symptoms of bradycardia	Decrease dose by 2.5mg (given twice daily); if current dose is 2.5 mg twice daily, then discontinue therapy

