### **5.4 Clinical Laboratory Results**

Descriptive summary of lab results of BNP and NT-proBNP will be presented by randomization arm over time. Moreover, summary change from baseline to 180 days will be presented by randomization arm. The data will be analyzed using the mixed model approach described in Appendix 2 after log transformation to correct the highly skewed nature of the data. A data listing of the lab measures BNP and NT-proBNP will be presented.

---

 The primary source of heart rate (at baseline and 180 days) is ECG assessment, if ECG assessment was not done at the 180 day visit, heart rate from vital signs assessment is used.

 BNP and NT-proBNP labs are deemed most relevant for this presentation.

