## **9.2 Secondary Analyses**

### **1. Heart Rate Assessments**

- a. Change in heart rate from baseline to 180 days will be compared across randomization groups. Change will be calculated as follows: (Baseline heart rate – 180 day heart rate). Comparisons across randomization groups will be performed using a linear model with adjustment for baseline heart rate and beta-blocker use. Randomization groups will be included in the regression model as main effect.

---

 Baseline beta-blocker use will be coded as a “0/1” variable with participants who received beta-blocker coded as “1” and those who did not receive beta-blocker as “0”.

 All change from baseline results presented are calculated similarly.

Heart rate is expected to be lower in the ivabradine arm than the usual care arm.  
Thus, change from baseline is expected to be higher in the ivabradine arm.

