### 9.3 Tertiary Analyses

1. Beta-blocker use at 180 days as assessed by the (a) proportion of participants on a beta-blocker at 180-days, (b) proportion on target dose, (c) proportion of participants who are at  $\geq 50\%$  target dose (d) the proportion discontinuing beta-blockers at 180 days and (e) the mean change in beta-blocker dose from discharge to 180 days will be compared between the randomization arms. - The mean change of beta-blocker dose will be calculated for participants who provide data at baseline and at 180 days post-discharge visits.

The proportions of participants on beta-blocker, the proportions on target dose, the proportion on at least 50% of the target dose, and the proportions discontinuing beta-blocker at 180 days will be summarized by randomization arms and tested using the Chi-square test. The change in beta-blocker dose from discharge to 180 days will be summarized and compared using the Wilcoxon rank sum test.

2. Ivabradine use at 180 days as assessed by the (a) proportion of appropriate participants with any initiation of ivabradine at 180 days, (b) the proportion of appropriate participants at the maximum dose of ivabradine at 180 day (i.e., 7.5 mg

---

 Comparing the mean change in beta-blocker dose is interpreted as comparing the distribution of dose changes between the randomization arms.

twice daily), and (c) the mean dose of ivabradine achieved at 180 days will be compared between the randomization arms.

Participants who do not provide the 180 day visit data will be coded as failures (ivabradine=0 and dosage=0.0). The mean dose of ivabradine achieved will be calculated for participants who provide data at 180 days post-discharge visit and using imputed values for the participants who do not provide 180 day visit data. As a sensitivity analysis, data will also be analyzed on observed data without imputing missing values. In addition, ivabradine dosage will be summarized for participants on ivabradine at the 180 day visit.

The proportions of appropriate participants with any initiation of ivabradine and the proportion of appropriate participants at the maximum dose of ivabradine at 180 days will be summarized as incidences by the randomization arms and tested using the Chi-Square test. The dose of ivabradine achieved at 180 days will be summarized and compared using the Wilcoxon rank sum test.

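### SAP footnote 2, by implication, selects the denominators of tertiary endpoints 2a and 2b on day-180 heart rate, so their chi-square tests do not compare the groups as randomised

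*SAP*

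**What the plan says.** SAP section 2.5.3 restricts endpoints 2a and 2b to appropriate participants. Footnote 2 defines them: "Appropriate participants are defined as participants who have a sinus rhythm (participants excluding those with AF) and heart rate of" at least 70 bpm. It gives no time point and continues: "For participants missing 180 day ECG, results from the baseline ECG are used to determine appropriateness".

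Section 9.3 says that both proportions "will be summarized as incidences by the randomization arms and tested using the Chi-Square test".

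Other places bear on this:

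- **The selecting variable is an outcome.** Secondary endpoint 1(c) is "Proportion of participants with heart rate < 70 bpm at 180 days", and section 9.2, item 1(a), states: "Heart rate is expected to be lower in the ivabradine arm than the usual care arm".
- **Entry criteria.** Protocol 3.2, item 7, requires of every participant on the planned day of randomisation: "Must be in sinus rhythm with a resting heart rate" of at least 70 bpm.
- **Heart-rate source.** For the heart-rate endpoints, SAP footnote 5 says "if ECG assessment was not done at the 180 day visit, heart rate from vital signs assessment is used". Section 13.1 and Appendix 1, item 2, agree with it.
- **Derivations.** Appendix 1, items 1(c) and 1(d), derives any initiation and maximum dose with no restriction to appropriate participants.
- **Purpose.** Protocol 2.3 and SAP 2.2.3 ask that evaluations of ivabradine use take account of whether the indication was retained. Protocol 10.4 uses the term appropriate participants for 2a and 2b without defining it.

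**The concern.** A between-arm test has the protection of randomisation only if membership of the analysed set does not depend on what happened after randomisation. Here it appears to depend on the day-180 heart rate, which the drug is meant to lower. Someone who started ivabradine and fell to 62 bpm drops out of both numerator and denominator; a user whose rate stayed at 70 or above remains. Participants with no day-180 ECG are judged on an ECG from around entry, when nearly all of them qualified, so they remain whatever their later heart rate was.

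At stake is whether the 2a and 2b percentages and p-values can be read as effects of the strategy. Section 13.6 withholds p-values only from analyses outside the primary, secondary and tertiary endpoints, so these tests will be reported.

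**Working it through.** **1. Which ECG decides.** If the baseline ECG decided for everyone, the sentence on a missing day-180 ECG would do nothing. The text makes sense only if the day-180 ECG decides where it exists. This is an inference, since footnote 2 does not say it outright.

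**2. Inputs.** The plan gives no figure for 2a or 2b. Its total of 450 reproduces (207 per arm with continuity correction; 414/0.92 = 450) but concerns the primary endpoint. From the documents I take only day-180 use of 50% vs 35% (protocol 10.2) and 104 enrolled (SAP 2.3). All other inputs are assumptions.

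- u = share on drug at day 180; s = share who started and stopped.
- h = share of current users at 70 bpm or above: 0.2, 0.4 or 0.6.
- Share of those off drug at 70 bpm or above: 0.7.
- No missing ECG at first.

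Retained share D = u·h + (1 − u)·0.7. Endpoint 2a in the subset = (u·h + s·0.7)/D.

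**3. Endpoint 2a, unequal persistence.** On drug / stopped / never: 50/25/25% pre-discharge, 35/5/60% usual care. True initiation is 75% vs 40%, odds ratio (0.75/0.25)/(0.40/0.60) = 4.5.

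At h = 0.4: 0.375/0.550 = 68.2% vs 0.175/0.595 = 29.4%.

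| h | Pre-discharge | Usual care | Odds ratio |
|---|---|---|---|
| 0.2 | 61.1% | 20.0% | 6.3 |
| 0.4 | 68.2% | 29.4% | 5.1 |
| 0.6 | 73.1% | 36.8% | 4.7 |

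**4. When the odds ratio survives.** Write I for initiation, p for persistence, and k1, k0 for the probability of being retained on and off drug. The subset odds are I·(p·k1 + (1 − p)·k0)/((1 − I)·k0). If p, k1 and k0 are the same in both arms, the extra factor cancels. Check with persistence of two thirds in both arms (usual care u = 0.267, s = 0.133) and h = 0.4: 68.2% vs 32.3%, odds ratio 4.5. Both percentages move, but the odds ratio does not.

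**5. Equal initiation, unequal persistence.** True 60% vs 60% (50 on + 10 stopped vs 35 on + 25 stopped).

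| h | Pre-discharge | Usual care | Difference | Standard error |
|---|---|---|---|---|
| 0.2 | 37.8% | 46.7% | −8.9 points | 13.8 |
| 0.4 | 49.1% | 52.9% | −3.9 points | 13.0 |
| 0.6 | 56.9% | 57.9% | −1.0 point | 12.0 |

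Standard errors assume 52 per arm before selection. Every shift is smaller than its standard error.

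**6. Endpoint 2b.** Suppose 60% of all users are at maximum dose: true 30% vs 21%, a gap of 9 points. Let q be the share at maximum dose among users at 70 bpm or above, so that 2b = u·h·q/D. At h = 0.4:

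| q | Pre-discharge | Usual care | Gap |
|---|---|---|---|
| 0.3 | 10.9% | 7.1% | 3.9 points |
| 0.6 | 21.8% | 14.1% | 7.7 points |
| 0.9 | 32.7% | 21.2% | 11.6 points |

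The gap is q·(0.2/0.55 − 0.14/0.595) = 0.1283·q, which equals 9 points at q = 0.70. The break-even is 0.62 at h = 0.6; at h = 0.2 it exceeds 1, so the gap always narrows. Protocol Table 1 ties dose to rate (above 60 bpm: "Increase dose by 2.5 mg (given twice daily) up to a maximum dose of 7.5mg twice daily"), so q could be high because a persisting fast rate prompts titration, or low because the maximum dose brings the rate down. The documents do not settle which.

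**7. A second model.** Take day-180 rate as normal with SD 12, an off-drug mean of 75 or 80 bpm, a drop of 5 to 15 bpm in users, 0 to 20% of ECGs missing and retained, and initiation equal to day-180 use. Mean 75, drop 10 and none missing give k1 = 0.34 and k0 = 0.66, so 50% vs 35% becomes 33.8% vs 21.6%. The odds ratio stays at 1.86, as step 4 requires, but the difference narrows from 15.0 to 12.2 points. Over the whole range the difference is 9.3 to 14.6 points. With equal initiation of 50% but drops of 10 vs 5 bpm, the filter alone produces −4.8 to −9.2 points. With no drop there is no distortion.

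**8. Retained sample.** At h = 0.4 with 52 per arm: 52·0.550 + 52·0.595 = 28.6 + 30.9, about 60 of 104 (51 at h = 0.2, 68 at h = 0.6). If 10% or 20% of ECGs are missing and those participants are retained, about 64 or 68 remain at h = 0.4, and the odds ratio in step 3 is 5.0 or 4.9 instead of 5.1.

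**9. Fallback compared with the heart-rate rule.** A participant with a day-180 pulse of 62 and no ECG is below 70 for endpoint 1(c) but will normally count as at least 70 under footnote 2.

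**The case against.** The strongest reply is that the protocol asks for this kind of subset. Retained indication is by nature a post-baseline status, it is named in the tertiary objectives, and protocol 10.4 limits 2a and 2b to appropriate participants. That stands: the subset is legitimate as a description, and calling the all-randomised percentages true presumes a target that the protocol did not set for these endpoints. It does not follow that a chi-square test by arm within the subset is a randomised comparison.

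The time point is also inferred, and Appendix 1, items 1(c) and 1(d), shows no filter. This is correct, and it makes the SAP inconsistent about where the restriction applies.

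A reader might infer that every 2a and 2b percentage is wrong whenever ivabradine lowers heart rate. That is too strong. A fall that does not cross 70 bpm changes nobody's status, and at h = 0.4 and q = 0.825 the pre-discharge 2b is 0.165/0.55 = 30%, exactly the unselected value. Nor do the documents support a claim that the filter favours a particular arm or invalidates the tests: step 3 widens the gap, step 7 narrows it, and if the strategy changes neither use nor heart rate the test keeps its size.

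A reader might also want the day-180 pulse to replace a missing ECG here. That would align the rate rule with the heart-rate endpoints, but it would extend selection on the treated rate, and a pulse cannot establish rhythm.

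**Conclusion.** The point holds and is minor. Read in the only way that gives its fallback a function, footnote 2 chooses the 2a and 2b denominators on a post-randomisation outcome that the SAP expects treatment to change. The section 9.3 tests on that subset therefore do not compare the groups as randomised.

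The proportions can be distorted when the drug moves participants across 70 bpm. The size and direction of any between-arm bias are not determined by the documents; the figures above rest on assumed persistence, heart-rate response, dosing and missingness. For 2a the odds ratio is unchanged if those features, dosing aside, are equal in the arms. For 2b even the direction is open.

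One might infer that the trial's main result is compromised. It is not: the primary analysis covers all randomised participants, and mean dose (2c) carries no such filter. Only two exploratory tertiary endpoints are affected.

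**What to change.** - State the time point in footnote 2.
- Reconcile footnote 2 and section 9.3 with Appendix 1, items 1(c) and 1(d), so that it is clear where the restriction applies.
- Report 2a and 2b for all randomised participants, who met the rhythm and rate criteria at entry, and base the between-arm comparison on that version. Appendix 1 already derives the unfiltered variables.
- Keep the day-180 appropriate subset beside it, labelled as selected after randomisation and descriptive.
- Note that its baseline-ECG fallback differs from the day-180 vital-sign fallback used for the heart-rate endpoints.

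The cost is a few lines of text and one extra table from existing data. Addendum 2 shows that the database is locked and treatment unblinded, so the change has to be documented as post hoc, with both versions shown.

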### **3 DATA SOURCES**

Clinical data are collected within the IBM Clinical Development (IBM CD, formerly eCOS) database. Protocol deviation data are collected within the Clinical Trial Management System (CTMS) database.

### **4 PARTICIPANT DISPOSITION**

The number of participants randomized, the number who dropped out early and the number that completed the study will be summarized by randomization arm and overall.

### **5 DEMOGRAPHICS AND BASELINE CHARACTERISTICS**

#### **5.1 Demographics and Baseline Characteristics**

Participant demographics will be summarized by randomization arm using descriptive statistics (mean, SD, median, inter-quartile range, min and max) for continuous and counts (percentages) for categorical variables. Demographics will include age, sex, race and ethnicity. Baseline characteristics will include BMI, LVEF and number of prior HF hospitalization, medical history and baseline medications.

#### **5.2 Vital Signs and NYHA Class**

Participant vital signs will be summarized by randomization arm over time and analyzed with a mixed model approach, described in Appendix 2. Statistical test for the treatment and the

---

 Completers are participants who had an in-person day 180 visit.

treatment \* time interaction will be done. -The vital signs summarized include heart rate, systolic blood pressure, diastolic blood pressure and weight. NYHA class will be summarized by randomization arm in shift tables from baseline to worst post-baseline and baseline to 180 days. Improvement (worsening) will be evaluated using the Chi-Square test. Improvement is defined as moving from a higher NYHA class to a lower class from baseline. Worsening is defined as moving from a lower class to a higher class from baseline. A data listing of vital signs and NYHA class will be presented.

### **5.3 Medical History**

Detailed information from the relevant medical history is reviewed during screening for each body system. Incidences of medical diagnostic conditions found during assessment will be tabulated by randomization arm.

### **5.4 Clinical Laboratory Results**

Descriptive summary of lab results of BNP and NT-proBNP will be presented by randomization arm over time. Moreover, summary change from baseline to 180 days will be presented by randomization arm. The data will be analyzed using the mixed model approach described in Appendix 2 after log transformation to correct the highly skewed nature of the data. A data listing of the lab measures BNP and NT-proBNP will be presented.

---

 The primary source of heart rate (at baseline and 180 days) is ECG assessment, if ECG assessment was not done at the 180 day visit, heart rate from vital signs assessment is used.

 BNP and NT-proBNP labs are deemed most relevant for this presentation.

## **6 MEDICATIONS**

A summary of medication usage will be presented by randomization arm over time. The summary will show the frequencies and percentages of participants using the medications. Beta-blocker and Ivabradine doses taken will be summarized by randomization arm. Beta-blocker dose descriptive summary will be presented in Carvedilol equivalent unit. Reasons for not taking beta-blocker will be summarized as frequencies and percentages by randomization arm over time. Dose data will be analyzed using the mixed model approach described in Appendix 2. A data listing of the medications will be presented.

## **7 PROTOCOL DEVIATIONS**

Protocol deviations will be summarized as frequencies and percentages by deviation type on a participant basis. A data listing of protocol deviations will also be presented.

## **8 SAFETY ASSESSMENTS**

### **8.1 12-Lead ECG**

Summary of ECG findings will be presented by randomization arm by assessment time point. Specifically, frequencies and percentages of rhythm, and descriptive summaries of QRS duration and QTc interval will be presented at baseline and 180 days post-discharge. ECG data will be analyzed using the Wilcoxon rank sum test. A data listing of ECG findings will be presented.

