### 3.3 Exclusion Criteria

If a subject meets any of the following criteria, he or she cannot be enrolled in the study:

- 1) Documented plan for up-titration of beta-blocker in the following 4 weeks
- 2) Permanent atrial fibrillation or atrial flutter
- 3) Patients with recent atrial fibrillation or flutter defined by either precipitating the current HF hospitalization or occurring during the current HF hospitalization
- 4) History of untreated sick sinus syndrome, sinoatrial block, or second and third degree atrio-ventricular block
- 5) Pacemaker with atrial or ventricular pacing (except biventricular pacing)  $\geq 40\%$  of the time
- 6) Family history or congenital long QT syndrome
- 7) Recent myocardial infarction ( $< 2$  months prior to screening) [troponin elevation secondary to acute HF as determined by the clinician is not an exclusion]
- 8) Acute or chronic severe liver disease as evidenced by any of the following: encephalopathy, variceal bleeding, INR  $> 1.7$  in the absence of anticoagulation treatment
- 9) Creatinine clearance  $< 15$  mL/min within 48 hours of screening that was not due to acute kidney injury that resolved
- 10) Planned mechanical circulatory support within 180 days

PRIME-HF

- 
- 11) Pregnant or breastfeeding women. Women of child-bearing potential should use effective contraception
  - 12) Medical conditions likely to lead to poor non-cardiac survival at 180 days (e.g., cancer)
  - 13) Inability to comply with planned study procedures
  - 14) If the following medications are needed at inclusion or during the study:
    - a) Non-dihydropyridine calcium channel blockers (e.g., diltiazem and verapamil)
    - b) Class I anti-arrhythmics (e.g., quinidine, procainamide, lidocaine, phenytoin)
    - c) Strong inhibitors of cytochrome P450 3A4 (CYP3A4), including some macrolide antibiotics (e.g., clarithromycin, erythromycin), cyclosporine, antiretroviral drugs (e.g., ritonavir, nelfinavir), and systemic azole antifungal agents (e.g., ketoconazole, itraconazole), and nefazodone
    - d) Inducers of cytochrome P450 3A4 (CYP3A4) including St. John's wort, rifampicin, barbiturates, and phenytoin.
    - e) Treatments known to be associated with significant prolongation of the QT interval, including sotalol

---

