### **5.2 Baseline Evaluations**

At the baseline visit and the time of randomization (prior to administration of ivabradine), all study participants will undergo the following:

- History and physical examination
- Baseline heart rate assessment via ECG (if ECG not already obtained in screening)
- KCCQ and PGA

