### **13.2 General Analysis Conventions/Rules**

All analyzed continuous variables will be summarized using descriptive statistics including number of observations, mean, standard deviation, minimum, 25th percentile, median, 75th percentile, and maximum. All analyzed categorical variables will be summarized using frequency counts and percentages. Percentages are calculated out of non-missing values unless stated otherwise. Comparisons of continuous (or discrete ordered) variables between randomization groups will generally be tested using the Wilcoxon rank sum test. For the secondary endpoint (change from baseline of the measures), analyses will be conducted using the general linear model approach. For comparisons over more than 2 time points, when appropriate, mixed effects models will be used to account for correlation within participant observations and assess time-by-treatment interactions (see Appendix 2 for details). Tests of binomial outcomes between randomization groups will generally be done with a Chi-square statistic. Tests of treatment effects will generally be 2-sided, with type I error = 0.05. Interaction tests will generally be done at the 0.10. Statistical significance is determined at a  $\leq$  0.05 alpha level.

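### SAP 8.1 compares QTc and QRS between arms only by an unadjusted Wilcoxon test, with no arm difference or confidence interval, although a baseline ECG is scheduled for every participant

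*SAP*

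**What the plan says.** SAP 8.1 announces "frequencies and percentages of rhythm, and descriptive summaries of QRS duration and QTc interval", which "will be presented at baseline and 180 days post-discharge". The only between-arm rule follows: "ECG data will be analyzed using the Wilcoxon rank sum test". The section does not say whether the test is applied to day-180 values or to change, and it plans no estimate of the difference.

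Other sections bear on this as follows.

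- **Baseline ECG.** Protocol 5.2 lists "Baseline heart rate assessment via ECG" for all participants unless one was already done at screening. The schedule in protocol 5.5 marks an ECG at baseline and at day 180 and at no other visit.
- **SAP 13.2.** Its default is: "Comparisons of continuous (or discrete ordered) variables between randomization groups will generally be tested using the Wilcoxon rank sum test". The linear model in the same section is for the secondary endpoints.
- **SAP Appendix 2.** The mixed model is for measures taken at more than two time points, so it does not reach the ECG data.
- **SAP 9.2.** Heart rate, whose primary source is the ECG (SAP 13.1), is analysed by a linear model with arm, baseline heart rate and baseline beta-blocker use.
- **SAP 13.6.** Anything that is not a primary, secondary or tertiary endpoint is exploratory and descriptive, without p-values. SAP 2.5 lists none of QTc, QRS or rhythm as an endpoint.

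**The concern.** The SAP places the ECG under its safety assessments, and this is its only comparison of QTc and QRS between arms. The protocol treats QT as relevant to safety. It excludes participants with congenital long QT or a family history of it, and those who need "Treatments known to be associated with significant prolongation of the QT interval, including sotalol".

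A rank-test p-value does not tell a safety reader what size of QTc shift the data exclude. That matters more here because SAP 2.3 reports that enrolment stopped at 104 of a planned 450. A non-significant result at that size says little without an interval.

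Part of the remaining uncertainty could be removed with a measurement that is already scheduled. The SAP does this for heart rate from the same tracing but not for QTc or QRS. Section 8.1 also asks for a test where section 13.6 allows no p-value.

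**Working it through.** **The plan's own figure.** The documents give no SD, correlation, precision target or power for any ECG measure, so there is no ECG figure to reproduce. The stated total of 450 belongs to the primary endpoint. It does reproduce: 35% versus 50%, 85% power, two-sided 0.05 and a continuity-corrected chi-square test give 207 per arm, so 414 in total, and 414/0.92 = 450.

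**Inputs.** From the documents: 104 enrolled with 1:1 allocation, so about 52 per arm. Assumed: QTc SD 40 ms, approximately normal data, and a correlation r between baseline and day-180 values of 0.3 to 0.8.

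**Formulas.** The Wilcoxon test yields no interval, so the unadjusted difference in means stands in for its precision.

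- Day-180 values alone: 1.96 × SD × √(2/n) = 1.96 × 40 × √(2/52) = 15.4 ms.
- Adjusted for baseline: 15.4 × √(1 − r²).
- Change scores, in case the test is meant for change: 15.4 × √(2(1 − r)).

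| r | Day-180 only | Change | Adjusted | Adjusted versus day-180 only |
|---|---|---|---|---|
| 0.3 | 15.4 | 18.2 | 14.7 | 5% narrower |
| 0.5 | 15.4 | 15.4 | 13.3 | 13% narrower |
| 0.7 | 15.4 | 11.9 | 11.0 | 29% narrower |
| 0.8 | 15.4 | 9.7 | 9.2 | 40% narrower |

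Entries in the middle three columns are 95% half-widths in ms. Since 1 − r² = (1 − r)(1 + r) is never larger than 2(1 − r), the adjusted interval is no wider than the other two, whichever way section 8.1 is read.

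**Sensitivity.** Half-widths scale with the SD: unadjusted they are 11.5 ms at SD 30 and 19.2 ms at SD 50. The percentages do not depend on the SD. SAP 13.5 expects more than 10% of day-180 heart rate, KCCQ and PGA values to be missing, so 52 per arm is optimistic for the ECG. With an assumed 40 per arm and SD 40 ms, the half-width is 17.5 ms unadjusted and 16.7, 15.2, 12.5 and 10.5 ms adjusted at the four correlations.

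**Validity.** In simulations of 4,000 trials per setting (normal data, 52 per arm), type I error was close to 5% for both the Wilcoxon test on day-180 values and the baseline-adjusted model. For an assumed shift of 0.5 SD, power was 0.71 versus 0.72 at r = 0, 0.70 versus 0.75 at r = 0.3, 0.69 versus 0.82 at r = 0.5, and 0.69 versus 0.95 at r = 0.7. Leaving out baseline therefore costs information and does not distort the test.

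**The case against.** The strongest reply is that nothing here is invalid. In a randomized comparison an unadjusted Wilcoxon test is sound, and the gain from adjustment depends wholly on a correlation the documents do not give. Six months pass between the two ECGs, starting from an acute admission, with background therapy adjustable throughout, so a high correlation cannot be taken for granted. QTc and QRS are not endpoints, and the QT exclusions apply equally to both arms. The small sample is itself a major limit on precision. All of this stands, and it is why the range starts at r = 0.3, where the gain is only 5%. The reply does not touch the missing estimate and interval, which are absent at any correlation.

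A reader might also infer that the SAP ranks rhythm codes, since rhythm is named just before the loose term for ECG data in section 8.1, and that the rhythm result would then depend on arbitrary code order. The documents do not support this. Section 8.1 gives rhythm counts and percentages, section 13.2 keeps the Wilcoxon test for continuous or ordered variables, and the same section says "All analyzed categorical variables will be summarized using frequency counts and percentages". Read together, the test covers QRS and QTc. The wording leaves an ambiguity worth closing, not a stated error.

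**Conclusion.** The point holds as a matter of precision and reporting. SAP 8.1 gives QTc and QRS an unadjusted rank test with no arm difference and no interval, and no other section fills the gap. Baseline adjustment would narrow the 95% interval by about 5% to 40% for correlations of 0.3 to 0.8. At an assumed SD of 40 ms and 52 per arm, that is from ±15.4 ms to between ±14.7 and ±9.2 ms. At zero correlation the gain is nil. The SD and the correlation are assumptions, and the percentages rest on the correlation alone.

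It would go too far to call the planned test biased or its error rate inflated, and no primary, secondary or tertiary result changes. That section 8.1 ignores baseline is its literal reading, though it does not say so outright. The conflict between a test in section 8.1 and the bar on p-values in section 13.6 is in the text and needs no assumption.

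**What to change.** In SAP 8.1, replace the Wilcoxon sentence for QTc and QRS. Report the day-180 arm difference in each, with a 95% confidence interval, from a linear model containing arm and the baseline value of the same measure. If the values are skewed, fit the same model on ranks, and keep the difference in ms beside it because ranks carry no unit. Label these results descriptive and give no p-value, so that sections 8.1 and 13.6 agree.

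As a clarification only, state that the Wilcoxon test does not apply to rhythm, which stays tabulated as counts and percentages by arm.

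The cost is about two sentences and minor programming, with no new data. The small downside is that participants without a baseline value drop out of the adjusted model, so the number analysed should be shown. Addendum 2 records a decision taken after database lock and unblinding. If this change is also made after that point, it should be dated and described as such.
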